## 5 STUDY DRUG ADMINISTRATION

See Section 8 for a complete description of study drugs. Instructions for the preparation of study drugs will be provided in a Pharmacy Manual.

### 5.1 Selection of Lefamulin Doses

This is the first study with lefamulin in subjects with CABP. Based on results obtained from *in vitro*, animal and human experiments conducted to date, lefamulin is predicted to be well tolerated and efficacious in CABP. To further explore and validate these findings, a pharmacometric approach was employed to assess a lefamulin dosing regimen of 150 mg IV q12h for the treatment of subjects with CABP caused by *S. pneumoniae* or *S. aureus* (the dosing regimen being utilized in this Phase 3 study). This approach has been utilized previously to support dose selection decisions in antibacterial drug development (Bhavnani et al., 2005; Bhavnani et al., 2009; Van Wart et al., 2009). An oral dose of 600 mg q12h (also being used in this Phase 3 study) has been shown to provide similar exposure (e.g., AUC) as the 150 mg IV dose. Since the primary PD driver of lefamulin efficacy is total drug exposure (AUC), 600 mg q12h given as an oral tablet is expected to provide equivalent therapeutic coverage as the 150 mg IV q12h regimen.

A population PK model describing the disposition of lefamulin, non-clinical PK/PD targets for lefamulin activity against *S. pneumoniae* and *S. aureus* (derived from robust surveillance data for both pathogens), and Monte Carlo simulation were utilized to carry out PK/PD target attainment analyses.

The population PK model used to conduct Monte Carlo simulations was developed using PK data from 11 Phase 1 studies of subjects who received IV or oral lefamulin and 1 Phase 2 study of infected subjects with ABSSSI who received IV lefamulin. Importantly, this dataset includes data describing the disposition of lefamulin in epithelial lining fluid (ELF) (obtained from a Phase 1 study; the relevant site for treatment of CABP) as well as in subjects experiencing active infection (the Phase 2 ABSSSI study). Thus, the data used to construct the population PK model, the parameter estimates and associated variability incorporated into the Monte Carlo simulations are reflective of patients with CABP.

Non-clinical PK/PD targets were identified using PK/PD relationships for efficacy derived from data from a neutropenic murine-lung infection model. For these analyses, focus was given to median 24 h AUCELF/MIC ratio targets for *S. pneumoniae* and *S. aureus* associated with a 1-log10 CFU reduction from baseline as it has been demonstrated that patients with CABP who attain a 1-log10 CFU reduction from baseline have a higher rate of successful response compared to those patients who did not attain such PK/PD targets. Lastly, in order to make inferences about dose for patients with *S. pneumoniae* or *S. aureus* bacteremia arising from CABP, the above-described analyses were also carried out using 24 h fAUC/MIC ratio targets for a 1-log10 CFU reduction from baseline efficacy for both pathogens. The MIC distributions utilized were based on large, contemporary isolate libraries that represent > 1400 *S. pneumoniae* and > 5500 *S. aureus* isolates, accrued globally.

Percent probabilities of attaining the median  $AUC_{ELF}/MIC$  ratio targets associated with a  $1\text{-log}_{10}$  CFU reduction from baseline by MIC were 97.0 % at a MIC of 0.5  $\mu\text{g}/\text{mL}$  for *S. pneumoniae* and 99.4 % at a MIC of 0.25  $\mu\text{g}/\text{mL}$  for *S. aureus* (thus, covering  $\geq 99.5$  % of Northern America and EU or worldwide isolates for either pathogen).

The results obtained from PK/PD target attainment analyses using a population PK model describing the disposition of lefamulin, non-clinical PK/PD targets for lefamulin against *S. pneumoniae* and *S. aureus*, robust surveillance data, and Monte Carlo simulation support the selection of the lefamulin 150 mg IV q12h/ 600 mg PO q12h as well-tolerated, having a high probability of efficacy and an appropriate dosing regimen to be studied for the treatment of adult subjects with CABP.

## 5.2 Selection of Comparator

For hospitalized patients with CABP admitted to a general ward, the Infectious Diseases Society of America (IDSA)/American Thoracic Society (ATS) treatment guidelines recommend the use of an antipneumococcal fluoroquinolone. In addition, if MRSA is suspected, the IDSA/ATS recommend the use of linezolid (Mandell et al., 2007). Consistent with these expert, consensus guidelines, the comparator chosen for this study is moxifloxacin (with or without adjunctive linezolid; see Section 5.3). Moxifloxacin (IV/PO) is indicated for the treatment of CABP caused by *S. pneumoniae* (including multi-drug resistant isolates), *H. influenzae*, *M. catarrhalis*, methicillin-susceptible *S. aureus*, *Klebsiella pneumoniae*, *M. pneumoniae*, or *C. pneumoniae*. Moxifloxacin will be administered at a dose of 400 mg every 24 hours for 7 -10 days as recommended in the prescribing information (Moxifloxacin SPC [solution], 2012; Moxifloxacin SPC [tablet], 2014). No dose adjustment of moxifloxacin will be permitted in this study. Subjects may be switched to oral moxifloxacin 400 mg once daily if, after receiving a minimum of 6 IV doses (3 IV moxifloxacin and 3 IV placebo), it is deemed clinically appropriate (see Section 5.5.3).

## 5.3 Adjunctive Treatment with Linezolid

As part of the Screening evaluation, the Investigator will determine whether MRSA is a probable pathogen in the subject. MRSA should be considered a potential cause of CABP when a good quality sputum Gram's stain shows both polymorphonuclear leukocytes and abundant Gram-positive cocci in clusters, or if local epidemiology and recent clinical experience suggest it is prevalent in the community. Linezolid is provided as empiric therapy in subjects where MRSA is suspected as the pathogen until culture results are available. If MRSA is suspected, adjunctive linezolid therapy will be added to the moxifloxacin treatment group, while matching placebo will be added in the lefamulin group pending final culture results. Linezolid treatment or matching placebo will only be continued in the presence of a microbiological culture confirming the presence of MRSA. If cultures do not grow MRSA, linezolid (or matching placebo) will be discontinued and subjects will be continued on moxifloxacin (or lefamulin).

Overall, it is anticipated that the proportion of subjects receiving adjunctive linezolid therapy would constitute the minority of enrolled subjects (e.g., <10%). Following receipt of

screening microbiological results, study drug therapy will be adjusted as described in Section 5.5.2.

Subjects for whom adjunctive therapy with linezolid is required will receive 600 mg IV q12h with potential switch to oral linezolid 600 mg q12h (see Section 5.5.3) (Linezolid SPC [solution], 2014; Linezolid SPC [tablet], 2014).

## 5.4 Randomization

Qualified subjects will be randomized to receive lefamulin or moxifloxacin in a 1:1 allocation ratio. Randomization may occur at either Screening or on Day 1 prior to receipt of the first dose of study drug. Subjects randomized to IV lefamulin will receive 150 mg of lefamulin q12h and subjects randomized to IV moxifloxacin will receive 400 mg of moxifloxacin q24h. In order to maintain the blind, subjects randomized to IV moxifloxacin will receive alternating doses of IV placebo administered q24h so that IV study drug is administered q12h.

Randomization will be stratified by PORT Risk Class (Risk Class III vs. IV and V; see Section 6.2), geographic region (US vs. ex-US), and prior (single dose) short-acting antibiotic therapy for CABP vs. none using blocked randomization via IRT. (NOTE: No more than 25% of randomized subjects will have received a single dose of a short-acting antibiotic). A minimum of 25% of the total number of subjects randomized will have a PORT risk class of IV or V.

The randomization schedule will be generated by Nabriva (or designee). Subjects randomized into the study will be assigned the treatment corresponding to the next available number in the respective stratum of the computer-generated randomization schedule. Prior to dosing, study personnel will contact the IRT system to obtain a treatment assignment. Subjects are considered randomized once a randomization number has been assigned regardless of whether the subject receives study drug. Randomized subjects who do not receive study drug or who discontinue participation in the study for any reason will not be replaced.

## 5.5 Study Drug Treatment

### 5.5.1 Duration of Treatment

It is estimated that the duration of blinded study drug administration for the majority (~90%) of subjects will be 7 days of active treatment as shown in Table 4 (Section 5.5.4). Subjects with CABP due to MRSA will receive 10 days of active treatment as shown in Table 5 (Section 5.5.4). Subjects with CABP due to MRSA, or those with confirmed *S. aureus* bacteremia will have their treatment adjusted as described below

### 5.5.2 Post-Baseline Treatment Modifications

Following receipt of the screening microbiological results, the following treatment modifications will be made. The investigator (or designee) must communicate culture results

in a timely manner to the unblinded pharmacist so that study treatment can be adjusted accordingly:

- Subjects who were suspected to have MRSA at Screening, and whose microbiological results confirm MRSA as a causative pathogen during the IV treatment period will be managed as follows:
  - Subjects randomized to receive moxifloxacin: IV moxifloxacin should be discontinued and linezolid will be continued for 10 days as shown in Table 5 below.
  - Subjects randomized to receive lefamulin: IV linezolid placebo should be discontinued and lefamulin will be continued for 10 days as shown in Table 5 below.
- Subjects who were suspected to have MRSA at Screening and whose microbiological results confirm MRSA as a causative pathogen during the oral treatment period will be managed as follows:
  - Subjects randomized to receive moxifloxacin: Oral moxifloxacin should be discontinued. Subjects will continue to receive oral linezolid plus oral lefamulin placebo to complete 10 days of study drug therapy as shown in Table 5 below.
  - Subjects randomized to receive lefamulin: Oral moxifloxacin placebo should be discontinued. Subjects will continue to receive oral lefamulin plus oral linezolid placebo to complete 10 days of study drug therapy as shown in Table 5 below.
- Subjects who were suspected to have MRSA at Screening and whose microbiological results do NOT confirm MRSA will have linezolid or matching placebo discontinued and will continue treatment with study drug for 7 days as shown in Table 4 below.
- Subjects whose microbiological results confirm *S. aureus* bacteremia (either methicillin-susceptible or methicillin-resistant) will be discontinued from study drug and have appropriate alternate therapy initiated promptly. If possible, blood samples should be collected and sent for microbiological culture prior to switching to alternate therapy.

NOTE: If a subject is determined to have an infection caused by MRSA plus an organism known to be resistant to linezolid, the Sponsor's medical monitor should be contacted.

If MRSA is confirmed as an etiological pathogen, but the subject was not prescribed adjunctive linezolid at Screening, the Investigator should assess the subject's clinical status at the time the microbiological results become available. If at this time the subject is demonstrating clear and progressive clinical improvement (e.g., improving temperature, respiratory signs and symptoms, etc.), then the subject may remain on blinded study drug therapy (i.e., lefamulin or moxifloxacin) and receive a total of 10 days of treatment. If not, then the subject should be discontinued from study drug therapy and appropriate alternative therapy initiated promptly. Linezolid or matching placebo cannot be added as study drug therapy subsequent to Day 1.

Similarly, if local laboratory susceptibility results from the screening cultures reveal resistance to a fluoroquinolone or linezolid, the Investigator should assess the subject's clinical status at the time the microbiological results become available. If at this time the subject is demonstrating clear and progressive clinical improvement (e.g., improving

temperature, respiratory signs and symptoms, etc.), then the subject may remain on blinded study drug therapy. If not, then the subject should be discontinued from study drug therapy and appropriate alternative therapy initiated promptly.

### 5.5.3 Optional Switch to Oral Study Drug

Subjects will be permitted to switch from IV to oral study drug (i.e., lefamulin or moxifloxacin ± linezolid or matching placebo) if all of the following criteria are met:

- Have received at least 6 doses of IV therapy;
- Are hemodynamically stable, as defined by a normalizing (including return to pre-pneumonia baseline) heart rate, respiratory rate, systolic blood pressure and oxygen saturation;
- Have a normalizing temperature curve with a maximum temperature in the previous 24 hours of <math><38.0^{\circ}\text{C}</math> (<math><100.4^{\circ}\text{F}</math>);
- Have demonstrated improvement in at least 1 severity category (e.g., moderate to mild) in at least 2 of 4 cardinal symptoms of CABP
  - Dyspnea
  - Cough
  - Sputum production
  - Chest pain;
- Are able to swallow and absorb oral medications (i.e., normally functioning gastrointestinal tract).

### 5.5.4 Treatment Scenarios

The treatment scenarios for IV plus oral study drug are outlined in the tables below.

**Table 4. CABP (not caused by MRSA)**

Study Drug	Regimen	Duration/Additional Dosing Information
Lefamulin	150 mg IV q12h	Total duration of blinded study drug = 7 days of active treatment. Days 1-3 = IV; Days 4-7 = IV or PO If IV study drug administration is switched to oral, moxifloxacin placebo will be administered q24h through Day 7.
	600 mg PO q12h	
Moxifloxacin	400 mg IV q24h	Total duration of blinded study drug = 7 days of active treatment. Days 1-3 = IV; Days 4-7 = IV or PO Separate, alternating doses of IV placebo will be administered q24h such that IV study drug is administered q12h; If IV study drug administration is switched to oral, lefamulin placebo will be administered q12h through Day 7.
	400 mg PO q24h	

NOTE: Subjects with confirmed *Staphylococcus aureus* bacteremia should have study drug discontinued and appropriate alternate therapy should be initiated promptly. If possible, blood samples should be collected for microbiological culture prior to switching to alternate therapy.

**Table 5. CABP (MRSA suspected at Baseline and confirmed Post-baseline)**

Study Drug	Regimen	Duration/Additional Dosing Information
Lefamulin	150 mg IV q12h	Total duration of blinded study drug = 10 days of active treatment. Days 1-3 = IV; Days 4-10 = IV or PO If IV study drug administration is switched to oral, moxifloxacin placebo will be administered q24h until an etiologic pathogen is confirmed (see below). Linezolid placebo q12h x 10 days (IV Days 1-3, IV or PO Days 4-10)
	600 mg PO q12h	
Moxifloxacin	400 mg IV q24h	Total duration of blinded study drug = 10 days of active treatment. Days 1-3 = IV; Days 4-10 = IV or PO Separate, alternating doses of IV placebo will be administered q24h such that IV study drug is administered q12h; If IV study drug administration is switched to oral, lefamulin placebo will be administered q12h Linezolid 600 mg q12h x 10 days (IV Days 1-3; IV or PO Days 4-10)
	400 mg PO q24h	

NOTE: If results of baseline respiratory tract cultures **do not confirm** MRSA as an etiological pathogen, then linezolid or matching placebo will be discontinued and the subject will complete 7 days of study drug as shown in Table 4 above.

NOTE: If results of baseline respiratory tract cultures **confirm** MRSA as an etiological pathogen **during the IV treatment period**, then IV moxifloxacin (for subjects in the moxifloxacin treatment arm) or IV linezolid placebo (for subjects in the lefamulin treatment arm) should be discontinued. If results of baseline respiratory tract cultures **confirm** MRSA as an etiological pathogen **after a subject has switched to oral treatment**, then oral moxifloxacin (for subjects in the moxifloxacin treatment arm) or oral moxifloxacin placebo (for subjects in the lefamulin treatment arm) should be discontinued.

NOTE: Subjects who are confirmed to have *Staphylococcus aureus* bacteremia should have study drug discontinued and appropriate alternate therapy should be initiated promptly. If possible, blood samples should be collected for microbiological culture prior to switching to alternate therapy.

NOTE: If a subject is determined to have an infection caused by MRSA **plus** an organism known to be resistant to linezolid, the Sponsor's medical monitor should be contacted.

## 5.6 Timing of Dosing and Dose Administration

Blinded IV study drug (lefamulin, moxifloxacin, linezolid, and matching placebo) will be administered approximately every 12 hours. Blinded IV lefamulin and moxifloxacin study drug doses will be infused over approximately 60 minutes. Blinded IV linezolid and matching placebo will also be infused over approximately 60 minutes. In subjects with suspected or confirmed MRSA, IV lefamulin and IV linezolid placebo or IV moxifloxacin and IV linezolid may be administered concurrently if two separate IV lines are used. If only one IV line is used, IV lefamulin and moxifloxacin should always be infused prior to linezolid or matching placebo.

The first dose of study drug will be administered on Day 1, as soon as possible after the diagnosis of CABP and completion of all required Day 1 procedures as outlined in Table 3; subsequent study days are consecutive calendar days. Every attempt should be made to administer 2 doses of study drug on Study Day 1. On Day 1, if q12h dosing is not feasible, the 1st and 2nd doses may be administered as close as 8 hours apart, in order to allow 2 doses to be given on Day 1. In this circumstance, the subject's dosing schedule should be adjusted on Day 2 to a regular q12h morning and evening schedule. Despite this, there may still be instances where it is not possible to administer 2 doses on Day 1. Subjects who receive only a single dose of study drug on Day 1 will receive their final dose in the morning on either Day 8 (to complete a 7-day course) or on Day 11 (to complete a 10-day course).

As described above, subjects randomized to the moxifloxacin treatment arm will receive IV moxifloxacin alternating with IV placebo to maintain the blind. Subjects should always receive active IV moxifloxacin as the first dose on Day 1. Subjects who begin therapy in the evening on Study Day 1 and whose schedule does not permit a second dose on Day 1 should have their dosing schedule adjusted on Day 2, so that active IV moxifloxacin is given as part of the morning dosing on all subsequent days.

Example 1: If a subject begins therapy at 3pm on Day 1, a second dose may be given at 11pm on Day 1. The subject's dosing schedule may then be adjusted on Day 2 to a regular q12h schedule (e.g., 8am and 8pm dosing). In this scenario, subjects randomized to moxifloxacin will receive active IV moxifloxacin at 3pm and IV matching placebo at 11pm on Day 1.

Example 2: If a subject begins therapy at 5pm on Day 1, it is not possible to give a second dose on Day 1 within the 8 hour minimum between doses. Therefore, the subject will receive a single dose on Day 1, and then be adjusted on Day 2 to a regular q12h dosing schedule (e.g., 6am and 6pm dosing). In this scenario, subjects randomized to moxifloxacin will receive active IV moxifloxacin at 5pm on Day 1, active IV moxifloxacin again in the morning on Day 2 (e.g., 6am) and IV matching placebo in the evening on Day 2 (e.g., 6pm). Subjects who require a 7-day course of study drug and who receive only a single dose of study drug on Day 1 will receive their final dose in the morning on Day 8 (to complete a 7-day course). Subjects who require a 10-day course of study drug and who receive only a single dose of study drug on Day 1 will receive their final dose on Day 11 (to complete a 10-day course).

Oral study drug doses of lefamulin, linezolid or matching placebo are to be administered approximately q12h. Oral moxifloxacin (or matching placebo) should be administered approximately q24h. Oral moxifloxacin (or matching placebo for subjects in the lefamulin treatment arm) will always be given as part of the morning dosing.

Every effort should be made to maintain a q12h dosing schedule, about the same time each day. On days when this is not feasible, doses should be given within 4 hours of the scheduled dosing time (i.e., a minimum of 8 hours between doses).

Oral study drug should be administered at least 1 hour before a meal or 2 hours after a meal. However, in the event that a subject has taken any of the following – antacids containing aluminum, products containing iron, or multivitamins containing zinc – study drug should be administered 2 hours before or 4 hours after consuming any of these medications. Oral doses should be administered with approximately 240 mL (8 ounces) of water.

The lot numbers and expiration dates of all study drugs supplied will be recorded.

Infusions will be administered via an infusion set and IV catheter at a controlled rate over approximately 60 minutes.

Subjects are not required to be hospitalized for entry into the protocol; however, while subjects are hospitalized, all doses of study drug will be administered by hospital staff or study personnel. Subjects may receive IV dosing as an outpatient; however, all IV dosing should be administered by hospital staff or study personnel (i.e., subjects are not permitted to self-administer IV study drug). In the event the subject is discharged from the hospital during the oral study drug administration period, subjects may self-administer oral study drug at home (see Section 5.10).

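### With a single Day 1 dose, the Day 8 stop in Section 5.6 gives 7 days of lefamulin but 8 active moxifloxacin doses, and Table 4 has no Day 8 dosing

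*Protocol*

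**What the plan says.** Protocol Section 5.6 asks sites to try for two doses on Day 1, at least 8 hours apart, and accepts that this will not always be possible. Subjects with a single Day 1 dose "will receive their final dose in the morning on either Day 8 (to complete a 7-day course", or on the morning of Day 11 for a 10-day course. The synopsis and footnote w of Table 3 repeat the rule.

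In the moxifloxacin arm the first Day 1 dose is always active. The schedule is then shifted on Day 2 "so that active IV moxifloxacin is given as part of the morning dosing on all subsequent days". For oral treatment, "Oral moxifloxacin (or matching placebo for subjects in the lefamulin treatment arm) will always be given as part of the morning dosing".

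Table 4 (Table 1 in the synopsis) covers pneumonia not caused by MRSA. For both arms it states "Total duration of blinded study drug = 7 days of active treatment" and "Days 1-3 = IV; Days 4-7 = IV or PO". After an oral switch, in the lefamulin arm "moxifloxacin placebo will be administered q24h through Day 7". In the moxifloxacin arm, "If IV study drug administration is switched to oral, lefamulin placebo will be administered q12h through Day 7". There is no footnote or exception for a Day 8 dose.

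Section 5.2 describes the minimum of six IV doses in the moxifloxacin arm as three active and three placebo.

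**The concern.** The Day 8 rule completes a 12-hourly course whose first half-day was missed. Moxifloxacin is given once daily, its Day 1 dose is already active, and the shift to mornings brings the next active dose forward. Applying the same Day 8 stop to both arms therefore cannot give the same number of treatment days in each.

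Two things are at stake. First, a site cannot tell from the protocol how many active comparator doses make up the stated course, or whether the last dosing day is Day 7 or Day 8. The end-of-treatment and test-of-cure windows both run from the last dose, so the choice moves them by a day. Second, for a subject on oral drug, Table 4 ends the dummies a day before the final dose in Section 5.6. Test of cure carries the investigator-assessed response that is the EMA primary variable, so the dummy instruction should be unambiguous.

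**Working it through.** **Inputs.** Table 4: lefamulin every 12 hours, moxifloxacin every 24 hours, 7 days of active treatment, Days 1 to 7. Section 5.6: final dose on Day 8 morning after a single Day 1 dose; first dose and all later morning doses active in the moxifloxacin arm. Example 2: start at 17:00 on Day 1, then 06:00 and 18:00.

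**1. Usual schedule, two doses on Day 1.** Dosing slots: 7 × 2 = 14.
- Lefamulin: 14 / 2 = 7 days.
- Moxifloxacin: 7 active + 7 placebo = 7 days.

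Table 4 is reproduced in both arms.

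**2. Single Day 1 dose, final dose on Day 8 morning.** Slots: 1 + (2 × 6) + 1 = 14.
- Lefamulin: 14 / 2 = 7 days, as stated.
- Moxifloxacin active: 1 (Day 1) + 6 (mornings of Days 2–7) + 1 (Day 8) = 8; placebo: 14 − 8 = 6.

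The excess over Table 4 is one active dose: 1/7 = 14%.

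**3. Single Day 1 dose, stopping on Day 7 as Table 4 reads.**
- Lefamulin: 1 + 12 = 13 doses, or 6.5 days.
- Moxifloxacin active: 1 + 6 = 7 doses.

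Neither stopping day gives 7 days in both arms.

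**4. Elapsed time on the Example 2 clock.** From 17:00 on Day 1 to 06:00 on Day 8 is 7 × 24 + 6 − 17 = 157 hours. Adding one dosing interval after the last dose:
- Lefamulin: (157 + 12) / 24 = 7.04 days.
- Moxifloxacin: (157 + 24) / 24 = 7.54 days.

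The extra active dose adds about half a day of coverage relative to lefamulin.

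**5. First six IV doses in the moxifloxacin arm.** They fall on Day 1 evening, Day 2 morning and evening, Day 3 morning and evening, and Day 4 morning. Four are active and two are placebo, against three and three in Section 5.2.

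**6. Ten-day course with a single Day 1 dose.** Slots: 1 + (2 × 9) + 1 = 20. A subject who stayed on moxifloxacin throughout would get 1 + 9 + 1 = 11 active doses.

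**7. Who is affected.** With an 8-hour minimum, a second Day 1 dose is impossible if the first is given after 16:00 (16 + 8 = 24). The protocol gives no distribution of start times. As an assumed range only, 10% to 50% of 550 would be 55 to 275 subjects. With 1:1 allocation, about 28 to 138 of them would be in the moxifloxacin arm.

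**The case against.** The best defence is that Table 4 is the nominal schedule and Section 5.6 is a deliberate exception, repeated in the synopsis and in footnote w of Table 3. Example 2 spells out the close active doses on Days 1 and 2, so they are no oversight. Lefamulin gets exactly 7 days, and an extra comparator dose, if it did anything, would work against a finding of non-inferiority. All of this is fair. It does not make 8 once-daily doses equal 7 days, and Table 4 does not point to the exception.

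Four stronger readings are tempting, and the documents do not support them.

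- *The blind breaks on Day 8.* This means applying Section 5.6 to the active drugs and Table 4 to the dummies. Section 5.6 always pairs the morning oral moxifloxacin dose with matching placebo in the other arm. Section 5.8 requires double-dummy for all oral dosing. Section 8.6 packs lefamulin and moxifloxacin each with the other's dummy. Subjects still on IV receive covered infusions.
- *Section 5.2 is breached on duration.* It says: "Moxifloxacin will be administered at a dose of 400 mg every 24 hours for 7 -10 days as recommended in the prescribing information". Eight daily doses fit that range. Only the three-and-three parenthetical fails, and the six-dose minimum still holds.
- *Every 10-day course has 11 moxifloxacin doses.* When MRSA was suspected at Screening and is then confirmed, moxifloxacin is stopped and linezolid every 12 hours continues: 1 + 18 + 1 = 20 doses, or 10 days. The 11-dose case arises only for subjects kept on moxifloxacin for 10 days under Section 5.5.2, where MRSA is confirmed without linezolid having been started and the subject is improving.
- *A third to a half of subjects are affected.* Those shares follow from assuming uniform start times over 24 hours (8/24 = 33%) or from 08:00 to midnight (8/16 = 50%). The protocol gives no such distribution and asks for every attempt at two Day 1 doses.

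**Conclusion.** The contradiction stands. For a subject with a single Day 1 dose, Section 5.6 gives 14 lefamulin doses but 8 active moxifloxacin doses under a stated 7-day course, and Table 4 has neither a Day 8 dose nor a Day 8 dummy. The size is one active comparator dose, about half a day of coverage on the Example 2 times, and only in the moxifloxacin arm. The count assumes that the morning-active rule is followed through Day 8, as written.

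On blinding, the finding is limited to disagreeing written instructions for subjects switched to oral drug; actual unblinding is not shown. The number of subjects affected is unknown. The point is still worth correcting, because the protocol itself anticipates the situation and the remedy is cheap.

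**What to change.** Reconcile Section 5.6 including Example 2, its synopsis counterpart, footnote w of Table 3, Tables 1 and 4, and the parenthetical on six IV doses in Section 5.2. For a subject with one dose on Day 1, these should agree on:

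- the number of active and placebo doses in each arm;
- the last day of active dosing and the last day of dummy dosing.

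The two versions of Example 2 should also be aligned. The synopsis specifies the morning for Day 11 but not for Day 8, and the body does the reverse. Section 5.5.2 should be covered for the few subjects kept on moxifloxacin for 10 days.

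The cost is protocol and Pharmacy Manual wording, plus a check that blister supply covers the last dosing day. Which schedule is right is for the sponsor's clinical team; this review takes no position on it.
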